5.1.1.6 Subgroup Analyses

The primary and secondary efficacy LOCF data analyses will be analyzed separately for each group for each ITT population, as appropriate:

Age Group:

- 3 to < 6 years
- 6 to < 12 years
- 12 to < 17 years

Weight Category by Age Group:

- \leq 18 kg and 3 to \leq 6 years
- >18 kg and 3 to < 6 years
- <=25 kg and 6 to < 12 years
- >25 kg and 6 to < 12 years
- <=50 kg and 12 to <17 years
- >50 kg and 12 to <17 years

Sex:

- Male
- Female

Here the same analysis methodologies as the primary and secondary analyses will be applied for the ITT populations (See Section 5.1.1.1.3, CFB ANCOVA). ANCOVA will be performed for each subgroup if the sample size available is at least 14 subjects. The Wilcoxon signed-rank test will be used when the one-sample t-test is not valid (See Section 5.1.1.1.3, CFB one -sample t-test).

Additionally, analysis of other important subgroups may be provided as appropriate.

5.1.1.7 Interim Analyses

Not applicable.

5.1.2 Determination of Sample Size

Sample size was calculated for the protocol as originally designed (Pre-Amendment 3: double-blind, placebo-controlled treatment period followed by an open-label extension) as follows:

This study was planned to include a minimum of 96 pediatric participants aged 6 to < 17 years who have a diagnosis of detrusor overactivity associated with a neurological condition. The sample size was selected to provide an adequate number of participants to evaluate the safety and efficacy of oxybutynin chloride gel treatment in a pediatric population. Participants were randomized in a 1:1 fashion to oxybutynin chloride gel or placebo within each stratification level, which were based on age, weight, and sex. Estimates for the average change from baseline (CFB) in the percentage of catheterizations without a leaking accident as well as the standard deviation for this variable were taken from oxybutynin TDS in Study O03010. Assuming a common standard deviation of 28 for the CFB in the percentage of catheterizations without a leaking accident, a difference between treatment groups of 20 (assuming average for oxybutynin chloride gel = 25 and average for placebo = 5), and n = 48 participants per treatment group, there is 93% power to detect a statistically significant difference between treatment groups. Based on discontinuation rates from Study O03010, if we assume a 10% dropout rate, then there is 90% power to detect a statistically significant difference between treatment groups.

The open-label study (participants enrolled Post-Amendment 3) will include a minimum of 25 pediatric participants aged 3 to < 17 years (efforts will be made to enroll a greater number of participants aged 3 years to < 6 years) who have a diagnosis of detrusor overactivity associated with a neurological condition. This sample size is expected to provide a minimum of 10 participants with 14 weeks of exposure.

5.2 Changes in the Conduct of the Study or Planned Analyses

At the time of writing this SAP, there were no changes in study conduct from what is described in the protocol and protocol amendments. Changes to planned analyses from what was described in the protocol are detailed in this SAP as described in Section 5.2.2 below.

5.2.1 Changes in the Conduct of the Study

Not applicable.

5.2.2 Changes to Analyses Prior to Database Lock

Version	Date	Summary
1.0	24 Oct 2017	Original version
2.0	28 Mar 2022	 Exact (Clopper-Pearson) 95% CI, Exact unconditional 95% CI using the score statistic, and Cochran-Mantel-Haenszel (CMH) was added in Table 5-2 to analyze binary urodynamic variable (Presence (versus total absence) of involuntary detrusor contractions at > 15 cm H2O)
		 CFB Mixed Model was deleted from Table 5-2. All CFB Mixed model analyses have been replaced with CFB ANCOVA as reflected in Table 5-12
		 Study part was removed as a factor from the CFB ANCOVA models
		 Details of how urodynamic assessments will be analyzed have been added in Table 5-12
		 Section 5.1.1.2 was modified to clarify analysis populations presented in demographics tables.
		 Exact Kolmogorov-Smirnov test was added in Table 5-2 to compare whether distributions of efficacy endpoints between patients treated with oxybutynin chloride gel in the two parts (Pre-Amendment 3 and Post-Amendment 3) of the study are the same
		 Section 5.1.1.3.1 was modified to provide details on how efficacy endpoints will be analyzed based on whether the distributions of efficacy endpoints between patients treated with oxybutynin chloride gel in the two parts (Pre- Amendment 3 and Post-Amendment 3) of the study were the same or not
		 Updated Table 5-15 definition of treatment-emergent adverse events in double-blind period to distinguish between participants who enter the 8-week open-label period from those that do not

6. Data Handling and Analysis Conventions

6.1 Study Treatment Conventions

6.1.1 Analysis Days

Treatment days are defined as follows:

Table 6-1 Analysis Day Definitions

Term	Description
Treatment Day	Double-Blind Relative to first dose date in double-blind phase if analysis date ≥ first dose date in double-blind phase: • Day = analysis date - first dose date in double-blind phase + 1 ○ Day 1 = first dose date in double-blind phase If analysis date < first dose date in double-blind phase:
	Open-Label Relative to first dose date in open-label phase if analysis date ≥ first dose date in open-label phase: • Day = analysis date - first dose date in open-label phase + 1 ○ Day 1 = first dose date in open-label phase If analysis date < first dose date in open-label phase:

6.1.2 Missing/Incomplete Treatment End Date

If the investigator is unable to provide the treatment end date, treatment end date will be imputed to the last available dosing record date.

6.2 Analysis Visit Windows

6.2.1 Efficacy

The analysis visit windows for efficacy endpoints during Post-Amendment 3 open-label period are defined as follows:

Table 6-2 Efficacy Analysis Visit Definitions for Pre-Amendment 3 Double-Blind Treatment Period

Ana	lysis Phase	Analysis Visit (Derived)	Study Visit (CRF)	Window
nt	Period	Baseline	Visit 1/Visit 2	Treatment Day ≤ 1
atme	Freatment le-Blind P	Week 2	Visit 4	Treatment Day [2, 28]
Tre	Double-I	Week 6	Visit 6	Treatment Day [29, X¹] if patients enters open label period; Treatment Day ≥ 29 otherwise

¹ X = First dose date of open label period – first dose date of double blind period + 1.

Table 6-3 Efficacy Analysis Visit Definitions for Post-Amendment 3 Open-Label Treatment Period

Analysis Phase	Analysis Visit (Derived)	Study Visit (eCRF)	Window
Treatment	Baseline	Visit A/Visit B	Treatment Day ≤ 1
	Week 6	Visit D	Treatment Day ≥ 29of open-label
			treatment

6.2.2 Safety and Other Assessments

The analysis visit windows for safety and other assessment endpoints are defined as follows:

Table 6-4 Safety Analysis Visit Definitions for Pre-Amendment 3

Ana	lysis Phase	Analysis Visit (Derived)	Study Visit (CRF)	Window
		Baseline	Visit 1/ Visit 2	Treatment Day ≤ 1
	riod	Week 1	Visit 3	Treatment Day [2, 11]
	nd Per	Week 2	Visit 4	Treatment Day [12, 21]
nt	-Blir	Week 4	Visit 5	Treatment Day [22, 35]
Treatment	Double-Blind Period	Week 6	Visit 6	Treatment Day [36, X^1] if patients enters open label period; Treatment Day \geq 36 otherwise
		Week 8	Visit 7	Treatment Day [2, 35] of open- label treatment
	Open-Label Period	Week 14	Visit 8/ET	Treatment Day ≥ 36 of open-label treatment

¹ X = First dose date of open label period – first dose date of double blind period + 1.

Table 6-5 Safety Analysis Visit Definitions for Post-Amendment 3 Open-Label Treatment Period

Analysis Phase	Analysis Visit (Derived)	Study Visit (eCRF)	Window
Treatment	Baseline	Visit A/Visit B	Treatment Day ≤ 1
	Week 2	Visit C	Treatment Day [2, 28]
	Week 6	Visit D	Treatment Day [29, 56]
	Week 10	Visit E	Treatment Day [57, 84]
	Week 14	Visit F/ET	Treatment Day ≥ 85

The following general conventions for repeated or unscheduled assessments will apply unless otherwise specified:

- The latest non-missing assessment within any analysis window will be flagged as the analysis value for any summaries by analysis visit
- All postbaseline assessments will be considered for PCS categorization
- All assessments will be included in respective listings

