Safety will be evaluated by monitoring adverse events, physical examinations, vital signs, clinical laboratory evaluations, skin erythema at the application site, and a vision symptom questionnaire.

Study Population:

Pre-Amendment 3 included pediatric patients, from ages 6 years to < 17 years, who had a diagnosis of detrusor overactivity associated with a neurological condition and were using CIC to control bladder function. These patients were enrolled into the 6-week placebo-controlled treatment plus an 8-week open-label treatment phase of the study. Post-Amendment 3 enrollment will include pediatric patients from ages 3 years to < 17 years, who have a diagnosis of detrusor overactivity associated with a neurological condition and are using CIC to control bladder function, with an enrollment of a minimum of 25 patients. These patients will be enrolled in a 14-week open-label treatment phase (approximately 10 patients are expected to complete the 14 weeks).

Test Product, Dose, and Mode of Administration:

Oxybutynin chloride gel, 0.5 g, 0.75 g (starting dose for Pre- and Post-Amendment 3), or 1 g sachets, applied transdermally once daily to dry intact skin.

Comparator Product:

For Pre-Amendment 3: placebo gel

For Post-Amendment 3: no comparator

Duration of Treatment:

For Patients Enrolled Pre-Amendment 3: A 6-week placebo-controlled treatment period followed by an 8-week open-label period

For Patients Enrolled Post-Amendment 3: A 14-week open-label treatment period

Efficacy Assessment:

The primary efficacy endpoint is the change from baseline (CFB) to Week 6 of treatment or to the last observation carried forward (LOCF) in percentage of catheterizations without a leaking accident as recorded in the 2-day urinary diary.

Secondary endpoints include the CFB to Week 6 of treatment in the following:

Urinary diary endpoints (calculated from the 2-day urinary diary data):

- Average volume of urine collected per catheterization (for Pre-Amendment 3 population only)
- Average volume of urine collected at first (morning awakening) catheterization
- Average number of catheterizations per day

Pharmacodynamic Assessments:

Pharmacodynamics will be assessed for treatment under the Pre-Amendment 3 double-blind phase, treatment under the Post-Amendment 3 open-label study, and both groups where appropriate. Pharmacodynamics will be based on urodynamic testing. The following parameters will be evaluated:

- Maximal bladder capacity

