9.5.4 Early Termination Activities

Upon patient withdrawal/early discontinuation from the study, all evaluations scheduled at Visit F (Week 14 of treatment) should be completed at the termination visit. If the early termination visit occurs immediately after a visit in which a diary had been previously dispensed, the diary will be reviewed and collected.

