5.1.1.4.3 Clinical Laboratory Assessments

Clinical laboratory assessments will be summarized by treatment group, double-blind treatment/oxybutynin chloride gel sequence, or oxybutynin chloride gel only group, as applicable, and by analyte and visit for each safety population. Study Part is either Pre-Amendment 3 or Post-Amendment 3.

² Study part refers to pre-amendment 3 and post-amendment 3; pre-amendment 3 has both open-label and double-blind periods, post-amendment 3 has only open-label period.

³ AEs with onset more than 30 days after the last dose of study drug are excluded from analysis.

Table 5-17 Clinical Laboratory Summaries

Endpoint	Description	Timing	Methodology
Descriptives	Summary of change from baseline by laboratory	Visit F ¹ for Post-	CFB
	category and parameter in SI units and analysis	Amendment 3 and	descriptives
	visit	Visit 8 for Pre-	
	 Parameters specified in Section 6.4.2.2 	Amendment 3	
Descriptives	Summary of raw values by laboratory category	Visits A and F ¹	Continuous
	and parameter in SI units and analysis visit	for Post-	descriptives
	 Parameters specified in Section 6.4.2.2 	Amendment 3 and	
	-	Visits 1 and 8 for	
		Pre-Amendment 3	
Shift from baseline ²	Summary by laboratory category and parameter	End of Period	Shift analysis
	 Low, normal, and high categories 	within a Study	
	provided by the central laboratory	Part ²	
	• Parameters specified in Section 6.4.2.2		

¹ Pre-Amendment 3 Week 14 or End of Treatment within Pre-Amendment 3; Post-Amendment 3 Week 14 or End of Treatment within Post-Amendment 3

Laboratory assessments values meeting *any* of the PCS low or PCS high criteria specified in Section 6.4.2.1 will be identified as PCS in the laboratory data listing.

5.1.1.4.3.1 Potential Hy's Law

Potential Hy's Law criteria will be summarized by treatment group, double-blind treatment/oxybutynin chloride gel sequence, or oxybutynin chloride gel only group, as applicable, and visit for each open-label safety population as follows:

Table 5-18 Potential Hy's Law Summaries

Endpoint	Description	Timing	Methodology
Potential Hy's Law	Postbaseline assessment of the following	Study Period	Categorical
within 24-hour window	laboratory parameters based on blood draws	within Study Part ¹	descriptives
	collected within a 24-hour period:	, and the second	-
	• ALT or AST $\geq 3 \times ULN$ and		
	• TBL \geq 2 × ULN and		
	• $ALP < 2 \times ULN$		
Potential Hy's Law	Postbaseline assessment of the following	Study Period	Categorical

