5.1.1.4.4 Vital Signs

Vital signs will be summarized by treatment group, double-blind treatment/oxybutynin chloride gel sequence, or oxybutynin chloride gel only group, as applicable, and visit for each safety population as follows:

Table 5-19 Vital Signs Summaries

Endpoint	Description	Timing	Methodology
Descriptives	Summary of change from baseline by	Pre-Amendment 3	CFB
	parameter and analysis visit	Weeks 1 to 6; Post-	descriptives
	Parameters specified in Section 6.4.3.1	Amendment 3 Visits	
		B, C, D, E, and F ¹	
Descriptives	Summary of raw values by parameter and	Pre-Amendment 3	Continuous CFB
	analysis visit	all double-blind	descriptives
	Parameters specified in Section 6.4.3.1	visits; Post-	
		Amendment 3 Visits	
		A, B, C, D, E, and	
		F^1	
Descriptives	Summary of raw values and change from	Combined open-	Continuous CFB
	baseline by parameter and analysis visit	label period	descriptives
	Parameters specified in Section 6.4.3.1		

¹ Analysis visits defined in Section 6.2.2.

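### SAP Tables 6-4 and 6-5 map the early-termination visit to Week 14 but their day windows send earlier exits elsewhere, so Table 5-20 may leave out early leavers' only post-baseline physical examination

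*SAP*

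**What the plan says.** - **Windows (SAP 6.2.2).** In Table 6-5 the study visit Visit F/ET belongs to Week 14, with window "Treatment Day ≥ 85". The earlier Post-Amendment 3 windows are Days 2–28 (Week 2), 29–56 (Week 6) and 57–84 (Week 10). In Table 6-4, Visit 8/ET belongs to Week 14, with window "Treatment Day ≥ 36 of open-label" treatment; open-label Days 2–35 are Week 8.
- **Selection rule (SAP 6.2.2).** "The latest non-missing assessment within any analysis window will be flagged as the analysis value for any summaries by analysis visit".
- **Exit procedures (Protocol 9.5.4).** When a patient leaves early, "all evaluations scheduled at Visit F (Week 14 of treatment) should be completed at the termination visit". The Visit F list in Protocol 9.5.2.5 includes a physical examination.
- **Physical examination schedule.** Post-Amendment 3 it is done at Visits A and F (Protocol 9.7.4 and Appendix 1). Pre-Amendment 3 it is done at Visits 1 and 8/ET (SAP Appendix 1).
- **Physical examination table (SAP Table 5-20).** It counts patients normal at baseline who became abnormal, by analysis visit. The timing given is Visits 8 and F plus the combined open-label period, and a footnote refers to Section 6.2.2 for the visits.
- **Laboratory table (SAP Table 5-17, footnote 1).** Here Visit F is defined as "Post-Amendment 3 Week 14 or End of Treatment within Post-Amendment 3", with a matching phrase for Pre-Amendment 3. Table 5-20 has no such footnote.

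**The concern.** In Tables 6-4 and 6-5 the visit label and the day window on the same row disagree for anyone who leaves before the Week 14 window opens. Most safety measures are repeated at every visit, so an exit value moved to Week 2, 6 or 10 is still tabulated. Laboratory data have the end-of-treatment footnote. Physical examination has neither protection: the exit examination is normally the only post-baseline one an early leaver has, and Table 5-20 names only the final visit of each part.

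At stake is who is counted in a safety shift table. Its denominator is the patients evaluated at the visit who were normal, so an omitted early leaver drops out of both numerator and denominator. Two programmers following the SAP could produce different tables from the same data.

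**Working it through.** **1. Reproduce the window starts.** Take nominal day = 7 × week + 1, and window start = midpoint of adjacent nominal visit days.
- Post-Amendment 3: Visit E (Week 10) = Day 71 and Visit F (Week 14) = Day 99. Midpoint = (71 + 99)/2 = 85, as printed.
- Pre-Amendment 3 open-label: Visit 7 (study Week 8, open-label week 2) = Day 15 and Visit 8 (study Week 14, open-label week 8) = Day 57. Midpoint = (15 + 57)/2 = 36, as printed.
- SAP Table 6-1 restarts the day count at the first open-label dose. Counted from the first double-blind dose, the Pre-Amendment 3 window opens at about 42 + 36 = Day 78, against Day 85 in the other part.

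Both starts are ordinary midpoints for scheduled visits. What is missing is a rule for unscheduled exits.

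**2. Place exit examinations under each reading.**

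| Exit examination | Day window governs | Visit label governs |
|---|---|---|
| Post, Days 2–28 (e.g. Day 20) | Week 2 | Week 14 / Visit F |
| Post, Days 29–56 (e.g. Day 43) | Week 6 | Week 14 / Visit F |
| Post, Days 57–84 (e.g. Day 70) | Week 10 | Week 14 / Visit F |
| Post, Day 85 onward | Week 14 | Week 14 / Visit F |
| Pre, open-label Days 2–35 | Week 8 | Week 14 / Visit 8 |
| Pre, open-label Day 36 onward | Week 14 | Week 14 / Visit 8 |
| Pre, double-blind period | Weeks 1 to 6 | Week 14 / Visit 8 |

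The readings agree only on the two rows at or beyond the window start. SAP 6.2.2 also says that all post-baseline assessments are considered for PCS categorisation, but Table 6-9 defines PCS criteria for laboratory values only. That rule does not rescue physical examinations.

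**3. Size in Post-Amendment 3.** Inputs are a minimum of 25 patients (Protocol 11.1), the Synopsis expectation that "approximately 10 patients are expected to complete the 14 weeks", and the 10% dropout rate in Protocol 11.1. That rate was assumed for the original placebo-controlled design; applying it here is an assumption.
- Visit label governs: 0 of 25.
- Window governs, 10% leave early with an examination before Day 85: 0.10 × 25 = 2.5, so 2 to 3 patients.
- Window governs, all patients not expected to reach 14 weeks have an examination before Day 85: 25 − 10 = 15, and 15/25 = 60%.

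The last figure is an upper bound for 25 enrolled and 10 completing. Protocol 9.5.3 asks for exit assessments only if possible. The Synopsis also says that only a portion of patients continue beyond 6 weeks. The documents do not say whether those who stop then have a Visit F examination, and Visit D includes none.

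**The case against.** The best defence is that nothing is lost. Table 5-20 names study visits, the window tables label those visits Visit 8/ET and Visit F/ET, and the protocol treats Visit F and early termination as one visit (9.5.2.5 and Appendix 1). On that reading every exit examination is in the right row. The reading is reasonable, but Table 5-20's own footnote sends the programmer to 6.2.2, where the analysis visit is derived and the value is chosen within a window. The conflict therefore stands.

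A second defence is that the data do not vanish. SAP 6.2.2 keeps all assessments in listings. The combined open-label entry in Table 5-20 could be read as covering any post-baseline open-label examination, and the text above the table promises summaries by visit. Clinically relevant findings are also adverse events (Protocol 9.7.1), and events leading to discontinuation have their own summary. All of this stands and limits the consequence. A claim that these examinations appear nowhere would be wrong.

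A reader might also infer three stronger points that the documents do not support:
- **That the Day 36 versus Day 85 difference causes the loss.** It does not: the two days are on different clocks, and identical windows would leave the ET conflict in place.
- **That the omission biases the table toward no findings because leavers stop for tolerability.** The documents give no reasons for leaving, and some stops at Week 6 may be planned.
- **That a pooled Week 14 row misstates gel exposure.** The combined row of Table 5-19 ("Summary of raw values and change from" baseline) is by analysis visit, but no pooled Week 14 row is named. SAP 5.1.1.4.4 groups vital signs by double-blind treatment/gel sequence or gel-only group, as applicable, which would separate former placebo patients (nominally 8 weeks, 56 days, of gel at Visit 8) from the others (nominally 98 days).

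**Conclusion.** The concern holds as a conflict within the SAP with a bounded consequence. The ET label and the day window disagree for every exit before open-label Day 36 (Pre-Amendment 3) or Day 85 (Post-Amendment 3), and no rule says which prevails. If the window prevails, those exit examinations are outside the Visit 8 and Visit F rows of Table 5-20. The affected share of Post-Amendment 3 patients cannot be fixed from the documents: it runs from zero, through about 10%, to at most 60%, on the assumptions shown. For Pre-Amendment 3 no figure can be given. Protocol 9.5.4 describes Post-Amendment 3 activities, so the Pre-Amendment 3 exit examination is inferred from the Visit 8/ET column of SAP Appendix 1. No direction of bias can be claimed. The table is descriptive, but the text should be settled before database lock because the same data can give two different tables.

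**What to change.** 1. Add an End of Treatment analysis visit to Tables 6-4 and 6-5, defined as the last on-treatment assessment, including ET.
2. State that for ET examinations this visit takes precedence over the day window.
3. Use it in Table 5-20 with a footnote modelled on Table 5-17 footnote 1, and say whether the combined open-label entry uses the same value.
4. Separately, confirm that the sequence grouping in SAP 5.1.1.4.4 also applies to the combined open-label row of Table 5-19. No more is needed on that point.

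The cost is a few lines of SAP wording and the programming of one derived visit. No new data are needed.

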6.3 Missing/Incomplete Date Conventions

Dates may be imputed with year, month, and day values under certain scenarios:

Table 6-6 Imputation Scenarios

		Complete					
Scenario	Year	Month	Day	Imputable			
1	Yes	Yes	Yes	Complete			
2	Yes	Yes	_	Yes			
3	Yes	_	Yes	No ¹			
4	Yes	_	_	Yes			
5	_	Yes	Yes	No ¹			
6	_	Yes	_	No ¹			
7	_	_	Yes	No ¹			
8		_	_	Yes			

¹ Not allowed per database design.

Dates will be imputed initially toward a specified target date for imputable scenarios 2, 4, and 8, and adjusted against the latest reasonable dates. The initial imputed date is determined by the following algorithm:

Table 6-7 Initial Imputed Date Algorithm

Available Year	Available Month (MM)						
(YYYY)	Missing	< Target Month = Target Month > Target Month					
Missing	Target Date	_					
< Target Year	YYYY-12-31	YYYY-MM-LD					
= Target Year	Target Date	YYYY-MM-LD Target Date YYYY-MM-01					
> Target Year	YYYY-01-01	YYYY-MM-01					

YYYY = available start date year; MM = available start date month; LD = last day of the month.

